2.2 Secondary Objectives

- To determine the effects of such inhibition on a range of hormones and metabolites: insulin, glucagon, amino and fatty acid levels, especially overnight.
- To determine the effects of such inhibition on plasma exosomes biomarkers related to ketone metabolism (such as MCTs, receptors, intracellular mediators of insulin signaling and ketone metabolism).
- To determine the effects of such inhibition on brain MRS measures of neuronal integrity and metabolism (NAA, glucose, lactate).
- To investigate if this age group will tolerate this class of anti-diabetic drugs, for re-purposing.

3 Study Design

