3.2 Study Endpoints

The primary study endpoint will be the level of circulating ketones on Visit 3 with a target of 1.5 times that of the participant's baseline (Visit 1). Other outcomes will be secondary.

4 Study Population

Twenty participants, ten males and ten females, age 55 and older will complete this pilot study. The ceiling for this study (100) reflects the additional accrual that we may anticipate. If needed, the protocol will be amended to account for an increase in the number of participants needed to be recruited.

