5.8 Early Termination Visit

The Principal Investigator may decide to take a participant off this study if it is believed to be in their best interest, if they fail to follow instructions, if new information becomes known about the safety of the study, or for other reasons the investigator believes are important. Participation in this study may be stopped at any time by the Principal Investigator without a participant's consent.

6 Study Procedures/Evaluations

Procedure	Screen	Visit 1	Visit 2	13 +/- 2 days post Visit 2	Visit 3
Informed Consent	X				
Review of Inclusion/Exclusion Criteria	X				
Medical History	X				
Physical Exam	X				
Height (cm) and Weight (kg)	X	X	X		X
Vital signs/orthostatic blood pressure measurements	X	X	X		X
CMP, ALT, AST, Alk. Phos., Total Bilirubin, CBC, Hepatitis B surface antigen, Hepatitis C, HIV and HbA1c, thyroid panel, cortisol level	X				
Urinalysis	X	X	X		X

Procedure	Screen	Visit 1	Visit 2	13 +/- 2 days post Visit 2	Visit 3
Blood samples for chemistry, lipids, oxysterols, lipodomics and exosomes (e.g., beta-amyloid)		X	X		X
CBC (Safety check)			X		X
Concomitant medication review	X	X	X		X
Insertion of venous catheter for frequent blood draws		X	X		X
Study medication (empagliflozin 25 mg daily)			X	X	X
Application of CGM		X	X		X
Diet Instructions / Record		X	X	X	X
Baseline blood and then frequent sampling (1.5-hours x 2, then q 1-hour x 1, then q 1.5-hours x 8, then q 2-hours x 4, then q 1.5-hours x 2, then q 1-hour x 1, then q 1.5-hours x 4. for β -hydroxybutrate (β -OHB), acetoacetate, fatty and amino acids, glucagon, insulin and glucose levels,		X	X		X
34-hour urine sampling for creatinine clearance, C-peptide and other hormones		X	X		X
MRS/MRI		X	X		X
Self-administration of study drug x 13 +/-2 days				X	
Meals/Snacks	X	X	X		X
Phone calls to monitor symptoms/compliance				X	
Adverse Event monitoring	X	X	X	X	X

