Empagliflozin (Jardiance) is an FDA approved drug used to treat type 2 diabetes. It is effective in lowering blood glucose levels in type 2 diabetic subjects, however, it is not known to lower blood glucose below normal levels (13). In other words, hypoglycemia is not a side-effect, it has not been reported to occur and is not therefore expected. An oral dose of 25 mg will be administered in the morning of days 1 and 2 of Visit 2. The participants will continue the study medication by self-administering for 13 +/- 2 days at home and recording on the medication log the time that they take their dose (Appendix G). The study medication will be discontinued at the end of Visit 3.

Diet Instructions/Records

Participants will be asked to record what they eat and drink during their inpatient visit on the Food Diary (Appendix C). They will be instructed on the importance of drinking 8 ounces of water every 4 hours, except when asleep. At discharge, they will be instructed to try and eat at the same times each day and record what time they eat or drink anything other than water on the Intake Diary (Appendix E).

Symptom Review Questionnaire

This will be used to assess the participant for any symptoms while taking the study medication. (Appendix I).

Compliance and symptom monitoring

Participants will be contacted daily between Visits 2 and 3 (during the days of self-administration of study drug) to ensure compliance and assess for any symptoms. We will also remind them about the importance of drinking water. It is imperative that participants do not miss 2 consecutive days of study medication or they will be excluded. The goal will be 100 percent compliance, however, greater than 90% will be acceptable.

Brain MRI: In total, structural MRI, fMRI and MRS will last about 1 hour.

- Structural MRI -- Standard structural brain images will be collected for coregistration, MRS voxel placement and to allow for clinical over-read.
- Resting state fMRI study in a single run. Subjects will be asked to keep their eyes open and fixate on a cross. This study will be used to assess intrinsic functional connectivity between different brain regions ⁶.

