9.2 Replacement of a Participant Who Discontinues Study Participation

Participants lost to follow-up, drop out, or are unable to participant any longer will be replaced at the discretion of the Principal Investigator.

10 Remuneration Plan for Subjects

The amount of payment to research volunteers is guided by the National Institutes of Health policies. In general, participants are not paid for taking part in research studies at the National Institutes of Health. Meals will be provided to participants.

Participants will be compensated for research-related discomfort and inconveniences in accord with NIH guidelines. Compensation of \$600 or more in one year will be reported to the IRS per federal regulation. The participants will be given 30 dollars at the Screening visit (Visit 0); The maximum amount allowable for the study is 1870 dollars, unless the study physician asks the participant to return to the NIA Clinical Unit for an unplanned visit. Then they will be paid an additional \$20 for each unplanned visit.

The participant will receive the following for completing each of the study visit:

Screening (Visit 0)	30 dollars
Visit 1	540 dollars
Visit 2	600 dollars
Visit 3	700 dollars
Unplanned Visit	20 dollars

The breakdown of payments is as follows:

Frequent blood sampling	140 dollars
Continuous Glucose Monitor	150 dollars
Food Diary (in-patient)	20 dollars (\$10/day)
Intake Diary (out-patient)	65 dollars
MRI	125 dollars
Activity Monitor/completing steps (in-patient)	25 dollars
34-hour urine collection	50 dollars
Study medication (self-dosing)	100 dollars

11 Study Monitoring Structure

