11.2 Safety Monitoring Plan

All protocols at the NIA follow the NIA Data and Safety Monitoring Plan. This includes using the Level of Risk Assessment Monitoring Guidelines that has been established for the NIA following NIH rules and regulations to ensure good clinical practices in the conduct of clinical research. Participants will be informed about new information from this or other studies that may affect their health, welfare, or willingness to stay in this study.

12 Statistical Considerations

This is a pilot study therefore no power calculation can be done.

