12.1 Participant Enrollment and Follow-Up

This is a pilot study of volunteers that consent to join the study. Potential participants who express the desire to be enrolled in the study are screened in the NIA Clinical Research Unit. Participants are enrolled once the informed consent is signed by the participant. Participants lost to follow-up, drop out, or are unable to participate any longer will be replaced at the discretion of the Principal Investigator.

13 Ethics/Protection of Human Subjects

Research conducted under this protocol will be conducted in compliance with the protocol, Good Clinical Practices (GCP) and all applicable regulatory requirements.

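### Could the tolerability result end up describing only the people who tolerated the drug?

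*Combined protocol and SAP*

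**What the plan says.** Section 2.2 lists tolerability among the secondary objectives: "To investigate if this age group will tolerate this class of anti-diabetic drugs, for re-purposing". Section 3.2 defines only the ketone endpoint and calls all other outcomes secondary, so tolerability has no stated measure or denominator.

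Section 12 opens with "This is a pilot study therefore no power calculation can be done" and otherwise covers enrolment and replacement. It names no analysis set. On sample size, Section 4 says: "Twenty participants, ten males and ten females, age 55 and older will complete this pilot study".

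Section 6.1, under compliance and symptom monitoring, makes two statements about missed doses. The first is a trigger: "It is imperative that participants do not miss 2 consecutive days of study medication or they will be excluded". The second is a level: full compliance is the goal, but "greater than 90% will be acceptable".

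Section 9.2 says that people who are lost, drop out or cannot continue "will be replaced at the discretion of the Principal Investigator", and Section 12.1 repeats the rule. Section 5.8 lets the investigator remove a participant for several reasons, among them "if they fail to follow instructions".

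**The concern.** A person who stops the drug because of side effects two or more days before Visit 3 has, on a literal reading, missed two consecutive days. If exclusion is taken to mean exclusion from the analysis, and that person is then replaced until twenty people complete, the outcome of interest itself causes removal from the denominator. The proportion stopping for intolerance would be zero by construction, and symptom rates would come from people selected for coping with the drug.

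This would matter because the protocol intends the pilot to inform a longer study in people with cognitive impairment. A flattering tolerability figure would carry into that design. The ketone ratio, for its part, would not show how many dosed people were missing from it.

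The adherence wording looks loose as well. Two separated missed doses can fall below the acceptable level without meeting the trigger, and the doses that form the denominator are not stated.

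**Working it through.** The plan gives no stopping rate, power or precision figure, and the twenty has no calculation behind it, so there is nothing to reproduce. The check has four parts.

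**1. What exclusion refers to.** The sentence stands in a procedures paragraph about compliance, not in the statistical section. The closest parallels concern participation: Section 5.8 is about taking someone off the study, and Section 7.1 puts out of the study anyone who is ineligible for the MRI or refuses it. Nothing in Section 12 or elsewhere says that an excluded person's data are dropped. Removal from further participation is therefore the ordinary reading.

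**2. Whether the data would exist.** The table in Section 6 marks adverse event monitoring at screening, at Visits 1, 2 and 3, and in the home-dosing period. Section 6.1 has staff telephone daily during home dosing, and Appendix I supplies the symptom form. Section 5.7 keeps samples after withdrawal, subject to the participant's right to restrict their use. Section 9.1 requires adverse events, non-compliance and deviations to be reported under NIH policy. A person who stops would have a record at least up to stopping.

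**3. Size if completers alone were summarised.** Assume k people stop for intolerance and all are replaced until 20 complete. The all-dosed proportion is k/(20 + k), with exact (Clopper-Pearson) 95% intervals. For a symptom, assume also that 4 of 20 completers report it and that every person who stopped had it, which is the worst case; the all-dosed rate is then (4 + k)/(20 + k).

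| k | Stopped, all dosed | Symptom, all dosed |
|---|---|---|
| 1 | 1/21 = 4.8% (0.1 to 23.8) | 5/21 = 23.8% (8.2 to 47.2) |
| 2 | 2/22 = 9.1% (1.1 to 29.2) | 6/22 = 27.3% (10.7 to 50.2) |
| 3 | 3/23 = 13.0% (2.8 to 33.6) | 7/23 = 30.4% (13.2 to 52.9) |

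The completers-only figures would be 0/20 stopping (0 to 16.8) and 4/20 = 20.0% with the symptom (5.7 to 43.7), whatever k is. The symptom rate is thus understated by 3.8, 7.3 or 10.4 percentage points, beside an interval 43.7 − 5.7 = 38.0 points wide.

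The chance that nobody among the first 20 dosed stops is (1 − p)^20. For assumed stopping rates this is 0.95^20 = 0.358 at 5% and 0.90^20 = 0.122 at 10%, so at least one stop has probability 0.642 or 0.878.

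**4. The two adherence statements.** With m missed of d doses, adherence is (d − m)/d. Section 6.1 gives 13 ± 2 days of home dosing, so d runs from 11 to 15.

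- One missed dose gives 10/11 = 90.9% to 14/15 = 93.3%, above 90%.
- Two missed doses give 9/11 = 81.8% to 13/15 = 86.7%, below it. Adding the four clinic doses to the longest period gives 17/19 = 89.5%, still below.
- If the interval in Section 5.5 is instead counted from Visit 2 Day 1 to Visit 3 Day 1, two of the 11 to 15 days are clinic days and d is 9 to 13. One missed dose then gives 8/9 = 88.9% or 9/10 = 90.0% at the two shortest lengths, and neither exceeds 90%.

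Two consecutive misses therefore meet the trigger and fall below the level; two separated misses only fall below the level. One statement sets a removal trigger and the other an acceptable level, and both can hold at once.

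**The case for a change.** The strongest case for a change is that collecting data does not settle who counts. Being a pilot explains the missing power calculation but not a missing denominator. The same investigator monitors safety (Section 11.1) and decides on replacement (Section 9.2), so the choice of denominator could be made after the results are known. The remedy would be a few lines of text with no new visits or tests. Even if exclusion means leaving the study, the document does not say whether the person's dosed days count towards tolerability.

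The textual part of this stands: the denominator is unwritten, and a completers-only summary is not expressly ruled out. The wide intervals in the table would not excuse such a summary either, since a stopping rate of zero by construction is wrong at any sample size.

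The inference to harm is weaker. It needs exclusion to be read as removal from the analysis, a discretionary replacement to be made, and recorded adverse events then to be left out of a report on whether this age group tolerates the drug. No section plans that last step. Someone who stops for side effects also falls more naturally under withdrawal (Section 5.7), removal by the investigator (Section 5.8) or drop-out (Section 9.2) than under a compliance rule, and missed days may have nothing to do with tolerability.

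For the ketone ratio there is little to gain. People who leave before Visit 3 have no Visit 3 value, so a rule to analyse all dosed participants with both visits would give essentially the set that would be analysed anyway. The documents define no adherent analysis group, so the adherence wording decides no planned analysis.

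**Conclusion.** The observation is accurate but does not call for a change. This is a definition left unwritten in a small single-arm pilot, and analysts would fill it in the usual way: adverse events, symptoms and discontinuations summarised over everyone who took a dose, with those who left or were replaced still counted and their reasons listed. The plan collects what that needs, and nothing in it directs otherwise.

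The possible distortion cannot be sized from the documents. It is zero if nobody stops or if all dosed participants are reported. With one to three stops, all replaced and left out, 4.8% to 13.0% of those dosed would be hidden; these figures are illustrations that rest on assumed stops, and the symptom figures also on a worst-case assumption.

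The conclusion rests on reading exclusion as leaving the study, which the parallel wording in Sections 5.8 and 7.1 supports. If a report did present completers alone as the tolerability result, the criticism would apply to that report. The two compliance statements in Section 6.1 should be read together, and no view is taken here on which should govern a participant's treatment.

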6.2 Laboratory Evaluations

6.2.1 Laboratory Samples

Blood Samples

Fasting blood samples are used to measure levels of chemicals, proteins, enzymes, inflammatory markers, markers of oxidative stress, lipids, minerals, hormones,

ketones and blood cells. Blood samples may include but are not limited to the following list.

Screen Visit: Fasting for at least 10 hours

- Comprehensive Chemistry Panel, ALT, AST, Alkaline Phosphatase, Total Bilirubin, thyroid panel
- Complete Blood Count (CBC) with Differential and Related Variables
- Hepatitis B surface antigen
- Hepatitis C antibody total
- HIV 1-2 antibody screen
- HbA1C
- Cortisol level
- Urinalysis

Visit 1

- Fasting Comprehensive Chemistry Panel, Lipids, oxysterols, lipidomics
- Exosomes (e.g., beta amyloid)
- β -hydroxybutrate (β -OHB), acetoacetate, fatty acids and amino acids
- Glucose, insulin and glucagon
- Urinalysis

Visits 2 and 3:

- Same as Visit 1, except CBC will be done for safety

Urine Sample

A 24-hour urine sample will be collected for creatinine clearance, C-Peptide and other hormones on Visits 1, 2 and 3.

6.2.2 Specimen Preparation, Handling and Shipping

Specimens are collected by research staff for clinical laboratory analysis and for research related to endocrinology and metabolism. No genetic testing will be performed.

All samples will be sent to the Core Lab via courier for pick-up by LCI staff.

Stored Samples: Samples of blood and tissue are stored in a deep freeze (-80 to -150°C). Samples are labeled with the participant's study identification code. All specimens collected are assembled in a "biological bank" of samples that are used by NIA to address questions related to the aims of this study. Samples used for exosome studies will be pulled and thawed once immediately prior to exosome isolation and biomarker determination at LNS.

The stored samples are kept indefinitely, controlled and managed by the Principal Investigator and the NIA. Study information is kept private to the extent possible by the law. Use of the biological samples is limited to designated NIA investigators or their collaborators under the auspices of the NIA Scientific Director and the

authorization and supervision of the PI. Strict privacy about the samples is maintained.

7 Potential Risks and Benefits

7.1 Potential Risks

Risks of Blood Drawing and Intravenous (I.V.) insertion: The total amount of blood taken during a screening visit is up to 30 milliliters (ml) or 2 tablespoons. The total amount taken for Visits 1, 2 and 3 will be about 504 ml or 34 tablespoons. Participants may experience some discomfort and/or bruising at the site of needle entry. There is a remote chance of fainting or infection. The I.V. may need to be inserted if unable to obtain frequent blood samples.

Risk of Stored Samples: The greatest risk from the use of stored samples is the unplanned release of information from medical records. The chance that this information will be given to an unauthorized person without the participant's permission is very small. We will not enter any experimental information (research results) into any other medical record and we will not release information to a third party unless specifically authorized by the participant. Possible problems with the unplanned release of information include discrimination when applying for insurance and employment. Some problems may occur if a participant discloses information or he or she agrees to have his or her medical records released.

Risk of Hepatitis Virus B, hepatitis virus C, and human immunodeficiency virus (HIV) Testing: This study involves a number of blood tests that require the subject's blood be tested for blood-transmitted diseases such as hepatitis virus B, hepatitis virus C, and human immunodeficiency virus (HIV). If the participant is infected with HIV, hepatitis B (positive HBsAG) or C (HCV RNA quantitative is detectable), he/she will not be able to participate in this study. We will tell the subject what the results mean, how to find care, how to avoid infecting others, how we report these infections, and the importance of informing any partners of possible risk.

Risks of Study Medication empagliflozin (Jardiance): The most common adverse reactions associated with administration of empagliflozin are dehydration, dizziness, lightheadedness, weakness, yeast and urinary tract infections. To decrease these risks, participants will be encouraged to hydrate and to maintain good hygiene. Other side effects may include low blood sugar, nausea, and upper respiratory tract infections. There also may be other side effects that we cannot predict, including hypersensitivity reaction. Rarely, sudden episodes of kidney injury may occur. Also, the Food and Drug Administration (FDA) has issued a warning about rare occurrences of a serious infection of the genital area (necrotizing fasciitis of the perineum) associated with sGLT2 inhibitors. Both of these have only been known in people who have diabetes. We will monitor for any symptoms during our daily calls to the participant while they are on study medication. This will include questioning any symptoms of tenderness, redness,

or swelling of the genitals or the area from the genitals back to the rectum. We will also monitor for fever or general feeling of being unwell.

Risks of Continuous Glucose Monitor (CGM): Potential risks include a slight skin irritation from the adhesive.

Risks of Brain MRI and MRS: The Food and Drug Administration (FDA) has recently established safety criteria for human exposure to MRI studies. The MRI scanner used in this study satisfies these safety criteria. People are at risk for injury from the MRI magnet if they have pacemakers or other implanted electrical devices, brain stimulators, dental implants, aneurysm clips (metal clips on the wall of a large artery), metallic prostheses (including metal pins and rods, heart valves, and cochlear implants), permanent eyeliner, implanted delivery pump, or shrapnel fragments. Welders and metal workers are also at risk for injury because of possible small metal fragments in the eye of which they may be unaware. Participants will be asked to complete an MRI screening form for each MRI. If any participant is found not to be eligible for the MRI or refuse the MRI, they will be disqualified from the study. In addition, all magnetic objects (for example, watches, coins, jewelry, and credit cards) will be removed before entering the MRI scan room. Participants with history of surgeries, implanted devices, etc. will be asked to provide us with surgical reports mentioning the type of the clips, prostheses, etc. used. Every effort will be made to establish the MR compatibility or incompatibility of these implants, according to the safety standards of the NIA 3T MRI center, including obtaining reports by manufacturing companies for MR compatibility. The research staff will evaluate each person with a less severe history of claustrophobia on a case-by-case basis.

Regarding minor discomforts, radiofrequency pulses emitted by the MRI machine can induce mild muscle twitching in some participants. If the sensation becomes overly uncomfortable, the scan will be stopped. The loud sounds (> 120 dB) emitted by the MRI machine during scanning require earplugs but may cause mild acoustic discomfort.

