5.3 Visit 1 Baseline – No study medication given

At Visit 1, the enrolled participant will come to the NIA Clinical Research Unit for a two-day visit, lasting approximately 34 hours. The following procedures will be done:

- a. Height/weight, orthostatic blood pressure measurements, pulse, temperature, respirations and pulse oximetry.
- b. I.V. placement for fasting blood tests (fasting for at least 8 hours) including CMP, lipids, insulin and other hormones, and exosomes. Followed by blood sampling every 1.5-hours x 2, then q 1-hour x 1, then q 1.5-hours x 8, then q 2-hours x 4, then q 1.5-hours x 2, then q 1-hour x 1, then q 1.5-hours x 4 (completes 34-hours). This frequent sampling will include β -hydroxybutrate (β -OHB), acetoacetate, fatty and amino acids, glucagon, insulin and glucose levels. On Day 2, exosomes will be repeated and oxysterols and lipidomics will be drawn.
- c. Placement of a continuous glucose monitor (CGM) used to collect data for up to 14 days, worn by the participant until they return for Visit 2.
- d. 34-hour urine collection for creatinine clearance, C-peptide, and other hormones.
- e. Brain MRS and limited brain MRI for voxel placement, required anatomical studies and resting functional connectivity will be conducted.
- f. All meals will be provided. The meals on visits 1, 2 and 3 will be pre-selected by the participant. Food intake will aim to be uniform at all visits and at consistent times. Participants will be asked to record the time and items they eat on a Food Diary (Appendix C). They will also be instructed to hydrate. This includes drinking 8 ounces of water every 4 hours except when asleep.
- g. On the evening of Day 1, the participants will be given an activity monitor and will be instructed to walk 2,000 steps before bedtime.
- h. Discharge instructions will be given (Appendix D). They will wear the CGM and be asked to complete an Intake Diary (Appendix E) to record consuming anything other than water to assist with the CGM data collection.

5.4 Visit 2 occurs 13 +/- 2 days from Visit 1

Initiation of sGLT2 inhibitor (empagliflozin)

At Visit 2, the enrolled participant will come to the NIA Clinical Research Unit for a two-day visit, lasting approximately 34 hours. This visit will be the same as Visit 1, except the participant will receive a daily dose of empagliflozin (Jardiance).

The following procedures will be done:

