- a. Height/weight, orthostatic blood pressure measurements, pulse, temperature, respirations and pulse oximetry.
- b. I.V. placement for fasting blood tests (fasting for at least 8 hours) including CMP, CBC, lipids, insulin and other hormones, and exosomes. The study drug empagliflozin (Jardiance) will be administered at approximately 8:00 a.m. followed by blood sampling every 1.5 hours x 2, then q 1-hour x 1, then q 1.5-hour x 8, then q 2-hours x 4, then q 1.5-hours x 2, then q 1-hour x 1, then q 1.5-hours x 4 (completes 34-hours). This frequent sampling will include β -hydroxybutrate (β -OHB), acetoacetate, fatty and amino acids, glucagon, insulin and glucose levels. On Day 2, exosomes will be repeated and oxysterols and lipidomics will be drawn.
- c. Placement of a continuous glucose monitor (CGM) used to collect data for up to 14 days, worn by the participant until they return for Visit 3.
- d. 34-hour urine collection for creatinine clearance, C-peptide, and other hormones.

- e. Breakfast will be given within 30 minutes of dosing.
- f. All meals will be provided. They will aim to be consistent items and times as what was consumed on Visit 1. Participants will be asked to record the time and items they eat on a Food Diary (Appendix C). They will also be instructed to hydrate. This includes drinking 8 ounces of water every 4 hours except when asleep.
- g. On the evening of Day 1, the participants will be given an activity monitor and will be instructed to walk 2,000 steps before bedtime. They will be instructed when they are discharged to continue to walk 2,000 steps every evening while wearing the activity monitor. This will occur during the time they are taking the study medication at home.
- h. Day 2: Participants will receive empagliflozin (Jardiance) 25 mg followed by breakfast within 30 minutes.
- i. Brain MRS and limited brain MRI for voxel placement, required anatomical studies and resting functional connectivity will be conducted.
- j. Following the final blood draw, participants will be sent home and instructed on self-administration of a daily morning dose of empagliflozin (Jardiance) 25 mg and will wear the CGM until returning for Visit 3.
- k. Discharge instructions will be given (Appendix F). They will wear the CGM and be asked to complete an Intake Diary (Appendix E) to record consuming anything other than water to assist with the CGM data collection.

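### Section 7.1 disqualifies a participant over the MRI with no limit by visit, so a refused or failed Visit 2 scan can cost the primary Visit 3 ketone endpoint for the sake of a secondary measure

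*Combined protocol and SAP*

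**What the plan says.** The rule is in Section 7.1, under the risks of brain MRI and MRS: "If any participant is found not to be eligible for the MRI or refuse the MRI, they will be disqualified from the study". The sentence before it reads: "Participants will be asked to complete an MRI screening form for each MRI". Neither names a visit.

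Sections 5.3, 5.4 and 5.5 each schedule a scan in the same words: "Brain MRS and limited brain MRI for voxel placement, required anatomical studies and resting functional connectivity will be conducted". The table in Section 6 agrees, marking MRS/MRI at Visits 1, 2 and 3. There is no drug at Visit 1. Under Section 5.4 the first dose comes on the first morning of Visit 2: "The study drug empagliflozin (Jardiance) will be administered at approximately 8:00 a.m".

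On priority, Section 3.2 says "The primary study endpoint will be the level of circulating ketones on Visit 3 with a target of 1.5 times" the participant's Visit 1 level, and adds "Other outcomes will be secondary". The imaging aim is in Section 2.2, among the secondary objectives: "To determine the effects of such inhibition on brain MRS measures of neuronal integrity and metabolism".

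Section 4.4 separately excludes people with an MRI contraindication at screening. Replacement of people who leave is left to the investigator's judgement (Sections 9.2 and 12.1). Section 5.8, headed as an early termination visit, lists no assessments. Section 12 defines no analysis set and no analysis method.

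**The concern.** Ketones are measured in blood and do not need a scan. Under the rule as worded, a secondary measure still decides whether a participant reaches the visit at which the primary endpoint is measured. Once a participant has been dosed, stopping because of a missed scan gives up the on-drug ketone data that the study is run to obtain.

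Two consequences would follow. Fewer of the 20 planned participants would contribute the Visit 1 to Visit 3 comparison. The loss might also be selective: Section 7.1 lists dizziness, lightheadedness, weakness and nausea among possible drug effects, and a session lasts about an hour (Section 6.1), so someone feeling unwell on drug might be more likely to decline it. That link is plausible, but nothing in the documents shows it. If it exists, a set made up of completers and replacements would lean towards people who tolerate the drug, and tolerability is itself a secondary objective in Section 2.2.

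**Working it through.** The plan gives no power, standard deviation, dropout rate or MRI refusal rate, so there is no figure of its own to reproduce. The check has two parts.

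**What an event at each scan costs, from the text**

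| Scan | Drug status | Effect of disqualification on the primary endpoint |
|---|---|---|
| Visit 1 | Before any dose | Participant lost, but not after dosing |
| Visit 2 | Dosing starts about 8:00 a.m. on Day 1; scan listed after the Day 2 dose, no clock time | Visit 3 does not take place, so the endpoint is lost |
| Visit 3 | After 13 ± 2 days; scan listed after the Day 2 dose and before the final draw, no clock time | Some or most ketone samples may already exist; their use is not stated |

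Only the Visit 2 event is a certain loss. A Visit 3 event is a possible loss.

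**Size, under stated assumptions**

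Inputs: 20 participants (Section 4), all assumed to reach the Visit 2 scan and otherwise to finish; one scan at each of Visits 2 and 3; an assumed probability *p* per scan of refusal or new ineligibility, independent between scans; no replacement.

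- Certain losses (Visit 2 only) = 20 × *p*
- Upper value (every Visit 3 event also costs the endpoint) = 20 × [1 − (1 − *p*)²]
- Chance of at least one loss among 20 = 1 − (1 − *p*)²⁰ for Visit 2 only, and 1 − (1 − *p*)⁴⁰ for both scans

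| Assumed *p* | Certain losses of 20 | Upper value of 20 | Chance of at least one: Visit 2 only | Chance of at least one: both scans |
|---|---|---|---|---|
| 2% | 20 × 0.02 = 0.4 | 20 × (1 − 0.98²) = 0.79 | 33% | 55% |
| 5% | 20 × 0.05 = 1.0 | 20 × (1 − 0.95²) = 1.95 | 64% | 87% |
| 10% | 20 × 0.10 = 2.0 | 20 × (1 − 0.90²) = 3.80 | 88% | 99% |

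Effect on precision: the half-width of a 95% t interval for a mean within-person change, in units of its standard deviation, is t(0.975, n − 1)/√n. This gives 0.468 at n = 20, 0.482 at n = 19, 0.497 at n = 18 and 0.533 at n = 16. Two losses therefore widen the interval by about 6% (0.497/0.468 = 1.06) and four by about 14% (0.533/0.468 = 1.14). With the rule confined to the period before dosing, losses from this cause after dosing are zero at any *p*.

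**The case against.** The strongest reply is that the rule concerns entry only. It speaks of the MRI in the singular, in a paragraph about implants and compatibility, and the infection-testing paragraph of the same section uses similar language for entry. That reading is possible. It is weakened by three facts: MRI contraindication is already a screening exclusion in Section 4.4; the screening procedures in Section 5.2 and the Section 6 table include no MRI form; and the rule directly follows the form repeated at each scan. If entry was meant, the protocol should say so.

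A second reply is that later refusals should be rare. Everyone reaching Visit 2 has passed the exclusion, any claustrophobia review and a drug-free scan, and some who refuse might have withdrawn anyway. This stands: the rates above are assumptions, and the loss due to the rule itself may be smaller. Refusal is still foreseeable, because Section 7.1 lets people with a milder history of claustrophobia be considered individually and allows an uncomfortable scan to be stopped, without saying whether stopping counts as refusal.

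A third reply is that imaging matters to the programme. Section 1.1 wants it to inform later outcomes and power analyses. That is a reason to collect scans, not to give up ketone data when one is missed.

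A reader might also infer that any missed scan after dosing deletes the primary endpoint and erases that person's tolerability data. The documents do not support this. At Visit 3, blood sampling begins before the point at which the scan is listed. Section 5.7 keeps samples usable after a withdrawal, and no section discards data from a disqualified participant. Adverse events are monitored at every stage in the Section 6 table and reported under Section 9.1, and symptoms are taken in the daily calls. What is collected before disqualification is not erased; its use in analysis is simply not stated. Nor does any section require a replacement to be someone who tolerates the drug.

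**Conclusion.** The point holds for Visit 2. As worded, the rule can remove a dosed participant before the primary endpoint because of a secondary measure. For Visit 3 the point is narrower: the protocol does not say whether ketone samples already drawn would be analysed. The Visit 1 scan precedes dosing and is not part of the concern.

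With 2%, 5% or 10% assumed per scan, the certain loss is about 0.4, 1.0 or 2.0 of 20, with upper values of 0.8, 2.0 or 3.8. These figures assume independent events, no replacement, and that those lost would otherwise have finished. Replacement can restore the count but not undo selection, if there is any. The effect on precision is modest. This is a cheap improvement to the plan; it does not invalidate the design.

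**What to change.** Amend Section 7.1 along these lines:

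> Disqualification for MRI ineligibility or refusal applies only before the first dose at Visit 2. After the first dose, a scan that is refused, not permitted by the screening form, or stopped early is recorded as missing imaging with the reason, and affects only the imaging analyses. MRI refusal or ineligibility alone does not end ketone and symptom data collection while the participant otherwise remains in the study. No one ineligible for MRI is scanned.

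Add to Section 12 that all available Visit 1 and Visit 3 ketone data enter the primary analysis, including data from participants with missing imaging.

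This wording concerns data collection and analysis. Decisions about study drug for such a participant are for the sponsor to reconcile with the other sections.

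The cost is a short amendment, a matching change to the consent form if it repeats the rule, and a few participants with incomplete MRS sets. If the sponsor intended the rule for entry only, the same text records that.
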